# Endocrinopathy Management Algorithm

[figure not shown]
Rule out non-inflammatory causes. If non-inflammatory cause, treat accordingly and continue I-O therapy. Consider visual field testing, endocrinology consultation, and imaging.

Patients on IV steroids may be switched to an equivalent dose of oral corticosteroids (e.g. prednisone) at start of tapering or earlier, once sustained clinical improvement is observed. Lower bioavailability of oral corticosteroids should be taken into account when switching to the equivalent dose of oral corticosteroids.

# Skin Adverse Event Management Algorithm

Rule out non-inflammatory causes. If non-inflammatory cause, treat accordingly and continue I-O therapy.

[figure not shown]
Patients on IV steroids may be switched to an equivalent dose of oral corticosteroids (e.g. prednisone) at start of tapering or earlier, once sustained clinical improvement is observed. Lower bioavailability of oral corticosteroids should be taken into account when switching to the equivalent dose of oral corticosteroids.

\*Refer to NCI CTCAE v4 for term-specific grading criteria.

^If SJS/TEN is suspected, withhold I-O therapy and refer patient for specialized care for assessment and treatment. If SJS or TEN is diagnosed, permanently discontinue I-O therapy.

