### **6.5.3.2 Dose Delays**

Dose delay criteria apply for all drug-related adverse events (regardless of whether or not the event is attributed to nivolumab, ipilimumab, or both).

Study therapy administration should be delayed for the following:

- Any Grade  $\geq 2$  non-skin, drug-related adverse event, with the following exceptions:
  - Grade 2 drug-related fatigue or laboratory abnormalities do not require a treatment delay
- Any Grade 3 skin, drug-related adverse event
- Any Grade 3, drug-related laboratory abnormality, with the following exceptions for asymptomatic amylase or lipase, AST, ALT, or total bilirubin:
  - Grade 3 amylase or lipase abnormalities that are not associated with symptoms or clinical manifestations of pancreatitis do not require a dose delay
  - If a participant has a baseline AST, ALT, or total bilirubin that is within normal limits, delay dosing for drug-related Grade  $\geq 2$  toxicity
  - If a participant has baseline AST, ALT, or total bilirubin within the Grade 1 toxicity range, delay dosing for drug-related Grade  $\geq 3$  toxicity
- Any adverse event, laboratory abnormality, or intercurrent illness that, in the judgment of the investigator, warrants delaying the dose of study medication

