### **6.5.3.3 Criteria to Resume Treatment**

Participants may resume treatment with study therapy when the drug-related AE(s) resolve to Grade  $\leq 1$  or baseline value, with the following exceptions:

- Participants may resume treatment in the presence of Grade 2 fatigue
- Participants with baseline Grade 1 AST/ALT or total bilirubin who require dose delays for reasons other than a 2-grade shift in AST/ALT or total bilirubin may resume treatment in the presence of Grade 2 AST/ALT OR total bilirubin
- Drug-related pulmonary toxicity must have resolved to baseline before treatment is resumed
- Drug-related endocrinopathies adequately controlled with only physiologic hormone replacement may resume treatment

If the criteria to resume treatment are met, the participant should restart treatment at the next scheduled timepoint per protocol. Doses should not be skipped.

If treatment is delayed  $> 6$  weeks (42 days) from the last dose due to drug-related toxicity, the participant must be permanently discontinued from study therapy, except as specified in Section 6.5.3.4. In the event treatment is

delayed > 6 weeks due to reasons other than study drug-related toxicity, the case should be discussed with the Principal Investigator before proceeding.

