#### **6.5.3.4 Discontinuation Criteria**

Treatment with study therapy should be permanently discontinued for the following:

- Any Grade 2 drug-related uveitis or eye pain or blurred vision that does not respond to topical therapy and does not improve to Grade 1 severity within the re-treatment period OR requires systemic treatment
- Any Grade 3 non-skin, drug-related AE lasting > 7 days, with the following exceptions:
  - Grade 3 drug-related uveitis, pneumonitis, bronchospasm, neurologic toxicity, hypersensitivity reaction, or infusion reaction of any duration requires discontinuation
  - Grade 3 drug-related laboratory abnormalities do not require treatment discontinuation except:
    - ◆ Grade 3 drug-related thrombocytopenia > 7 days or associated with bleeding requires discontinuation
    - ◆ Any drug-related liver function test (LFT) abnormality that meets the following criteria require discontinuation:
      - AST or ALT > 8 x ULN
      - Total bilirubin > 5 x ULN
      - Concurrent AST or ALT > 3 x ULN and total bilirubin > 2 x ULN
- Any Grade 4 drug-related AE or laboratory abnormality, except for the following events which do not require discontinuation:
  - Grade 4 neutropenia  $\leq$  7 days
  - Grade 4 lymphopenia or leukopenia
  - Isolated Grade 4 electrolyte imbalances/abnormalities that are not associated with clinical sequelae and are corrected with supplementation/appropriate management within 72 hours of their onset
  - Grade 4 amylase or lipase abnormalities that are not associated with symptoms or clinical manifestations, or radiographic signs of pancreatitis. It is recommended to consult with the Principal Investigator for Grade 4 amylase or lipase abnormalities
  - For Grade 4 endocrinopathy AEs such as adrenal insufficiency, ACTH deficiency, hyper or hypothyroidosis, or glucose intolerance, which resolve or are adequately controlled with physiologic hormone replacement (steroids, thyroid hormones) or glucose controlling agents, respectively, retreatment can be considered after discussion with the Principal Investigator
- Any dosing interruption lasting > 6 weeks from the last dose with the following exceptions:

- Dosing interruptions to allow for prolonged steroid tapers to manage drug-related AEs are allowed. Prior to re-initiating treatment in a participant with a dosing interruption lasting > 6 weeks from the last dose, the Principal Investigator must be consulted

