#### **6.5.4 Management Algorithms for Immuno-Oncology Agents**

Immuno-oncology agents are associated with AEs that can differ in severity and duration from AEs caused by other therapeutic classes. Nivolumab and ipilimumab are considered immuno-oncology agents in this protocol. Early recognition and management of AEs associated with immuno-oncology agents may mitigate severe toxicity. Management algorithms have been developed to assist investigators in assessing and managing the following groups of AEs:

- Gastrointestinal
- Renal
- Pulmonary
- Hepatic
- Endocrinopathies
- Skin
- Neurological

The recommendation is to follow the nivolumab algorithms for immune-oncology agents (I-O) in order to standardize the safety management across the study.

The algorithms are found in the Nivolumab Investigator Brochure and Appendix 2 of this protocol.

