## 9.4 Endpoints

### 9.4.1 Primary Endpoints

**Part I: Safety Run In Phase I:** Unacceptable toxicity status at the end of 13-week safety observation period with unacceptable toxicity defined as:

- Any grade 4 immune related adverse event (irAE),
- Any  $\geq$  grade 3 noninfectious pneumonitis,
- 
- Any grade 3 irAE, excluding pneumonitis, that does not downgrade to grade 2 within 7 days after onset of the event despite optimal medical management including systemic corticosteroids or does not downgrade to  $\leq$  grade 1 or baseline within 14 days,
- Liver transaminase elevation  $> 8 \times$  ULN or total bilirubin  $> 5 \times$  ULN,
- Any  $\geq$  grade 3 non-irAE, except for the following exclusions:
  - grade 3 fatigue lasting  $\leq$  7 days
  - grade 3 endocrine disorder (thyroid, pituitary, and/or adrenal insufficiency) that is managed with or without systemic corticosteroid therapy and/or hormone replacement therapy and the participant is asymptomatic
  - grade 3 infusion-related reaction (first occurrence and in the absence of steroid prophylaxis) that resolves within 6 hours with appropriate clinical management
  - grade 3 or 4 neutropenia that is not associated with fever or systemic infection that improves by at least 1 grade within 3 days.

**Part II: Phase II:** The primary endpoint is 6-month PFS status. PFS is defined as the duration from date of registration to date of first documentation of progression assessed by local investigator or symptomatic deterioration (as defined above) or death due to any cause. Patients last known to be alive without report of progression are censored at date of last disease assessment. For patients with a missing scan (or consecutive missing scans) whose subsequent scan determines progression, the expected date of the first missing scan (as defined by the disease assessment schedule) will be used as the date of progression.

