## 14 APPENDIX 2: MANAGEMENT ALGORITHMS FOR IMMUNE ADVERSE EVENTS

These general guidelines constitute guidance to the Investigator and may be supplemented by discussions with the Principal Investigator.. The guidance applies to all immuno-oncology (I-O) agents and regimens. A general principle is that differential diagnoses should be diligently evaluated according to standard medical practice. Non-inflammatory etiologies should be considered and appropriately treated. Corticosteroids are a primary therapy for immuno-oncology drug-related adverse events. The oral equivalent of the recommended IV doses may be considered for ambulatory patients with low-grade toxicity. The lower bioavailability of oral corticosteroids should be taken into account when switching to the equivalent dose of oral corticosteroids. Consultation with a medical or surgical specialist, especially prior to an invasive diagnostic or therapeutic procedure, is recommended. The frequency and severity of the related adverse events covered by these algorithms will depend on the immuno-oncology agent or regimen being used.

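### For a drug-related SJS/TEN event graded below 4, the Appendix 2 skin footnote and Sections 6.5.3.2 to 6.5.3.4 give conflicting instructions on holding, stopping and restarting study drug

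*Combined protocol and SAP*

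**What the plan says.** Appendix 2, Skin Adverse Event Management Algorithm, deals with SJS/TEN in a footnote. On suspicion: "If SJS/TEN is suspected, withhold I-O therapy and refer patient for specialized care for assessment and treatment". On diagnosis: "If SJS or TEN is diagnosed, permanently discontinue I-O therapy". Neither sentence states a grade.

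The body works by grade:

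- Section 6.5.3.2 lists among its reasons for delay "Any Grade 3 skin, drug-related adverse event". Its grade 2 trigger is confined to non-skin events.
- Section 6.5.3.3 allows resumption at grade 1 or below, or at baseline, with listed exceptions that do not mention SJS/TEN. Once the criteria are met, "the participant should restart treatment at the next scheduled timepoint per protocol. Doses should not be skipped".
- Section 6.5.3.4 requires permanent discontinuation for "Any Grade 3 non-skin, drug-related AE lasting > 7 days, with the following exceptions". It separately stops drug for any grade 4 drug-related event, and none of the exceptions to that rule is a skin event. It also stops drug for interruptions beyond six weeks, with exceptions, and for any event that the investigator judges too risky for further dosing.

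On standing, Section 4.6 makes the Section 6.5.3.4 criteria mandatory. Appendix 2 says of itself "These general guidelines constitute guidance to the Investigator", and Section 6.5.4 only recommends following the algorithms.

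**The concern.** Two parts of one protocol answer the same question differently: what happens to study drug when a patient has SJS or TEN that is not graded 4? An investigator working from the appendix stops for good. One working from Sections 6.5.3.2 to 6.5.3.4 may hold the dose, wait for resolution, and then find an instruction to restart.

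The plan does not say which text prevails. If a site settles the matter by standing, Section 4.6 gives force to the list without an SJS/TEN stop, while the text that contains the stop is described as guidance. At stake is patient safety, because the body permits re-dosing that the appendix rules out. Consistency across sites is also at stake, since two sites could handle the same event in opposite ways and each could cite the protocol.

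**Working it through.** No sample size, error rate or other stated figure is involved, so there is nothing to recompute. The check sets the texts side by side for a drug-related event. It takes SJS/TEN to be a skin event in the sense of Section 6.5.3, because the plan places it in the skin algorithm.

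| Situation | Appendix 2 skin footnote | Sections 6.5.3.2 to 6.5.3.4 | Result |
|---|---|---|---|
| Suspected, grade 3 | Withhold and refer | Delay | Agree on the hold |
| Suspected, below grade 3 | Withhold and refer | No grade-based delay for a skin event; hold only on investigator judgment | Differ |
| Diagnosed, grade 4 | Permanent stop | Permanent stop; no skin exception | Agree |
| Diagnosed, grade 3, back to grade 1 or baseline | Permanent stop | Delay, then restart, unless a judgment stop or the six-week rule applies | Conflict |
| Diagnosed, below grade 3 | Permanent stop | No grade-based delay or stop; judgment only | Conflict, if such grading occurs |

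The steps for the grade 3 diagnosed case are:

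1. Section 6.5.3.2 delays the dose.
2. The grade 3 rule in Section 6.5.3.4 does not reach it, because that rule is restricted to non-skin events.
3. The grade 4 rule does not reach it either.
4. On resolution, none of the exceptions in Section 6.5.3.3 singles it out, so the general restart instruction applies.
5. The footnote, applied to the same patient, has already ended treatment.

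Two comparisons suggest that the skin footnote was simply not carried into the body. Section 6.5.3.4 already names particular diagnoses that stop drug at grade 3 whatever their duration, such as pneumonitis, uveitis and neurologic toxicity. The hepatic footnote in Appendix 2 also uses the same limits as Section 6.5.3.4: 8 times the upper limit of normal for AST or ALT, and 5 times for total bilirubin. The SJS/TEN footnote has no such counterpart.

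**The case against.** The best reply is that the texts can be read together: the specific SJS/TEN sentence adds to general grade rules, and nothing in Section 6.5.3 forbids a permanent stop. Section 4.6 separately requires discontinuation when the investigator thinks that continuing is not in the participant's interest, and Section 6.5.3.4 has its own judgment stop. Section 6.5.3.3 first permits resumption, so its later restart sentence could be read as fixing timing only. A toxicity delay beyond six weeks usually ends treatment as well. Someone might also class the event as a hypersensitivity reaction, which Section 6.5.3.4 stops at grade 3.

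Much of this stands as mitigation, and a careful investigator would probably stop. It does not remove the conflict. The judgment stops are discretionary where the footnote is not. The six-week rule has exceptions, including for prolonged steroid tapers, and does not touch an event that resolves sooner. The hypersensitivity item sits under the non-skin criterion and does not name SJS/TEN.

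A second objection also stands in part. The skin flowchart is not shown, so it is not visible which grade box carries the footnote mark. All that can be said is that the footnote's own words contain no grade condition.

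A reader might go further and infer that the plan re-doses patients after a life-threatening reaction. The documents do not support that. Section 6.5.3.4 permanently stops any grade 4 drug-related event with no skin exception. The only place where the shown text ties the words life threatening to a grade is the infusion-reaction guidance, and the grade there is 4.

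**Conclusion.** The conflict is real but narrow. It concerns drug-related SJS/TEN graded below 4, and it is sharpest for a diagnosed grade 3 case that resolves. Grade 4 cases are stopped under both texts. The conclusion rests on reading the footnote as independent of grade, as its words suggest, and on SJS/TEN counting as a skin event in Section 6.5.3.

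No frequency can be attached. The documents give no SJS/TEN rate and do not reproduce the CTCAE grading of either condition, so how many cases would fall below grade 4 is unknown.

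A reader might also infer that the lead-in endpoint in Section 9.4.1 is wrong because a case that ends treatment under Appendix 2 could go uncounted. At grade 3, that could happen only for an immune-related event that escapes the criterion "that does not downgrade to grade 2 within 7 days after onset of the event despite optimal medical management including systemic corticosteroids" and also reaches grade 1 or baseline within 14 days. This is not an error in the plan, which nowhere says that every event ending treatment must count as unacceptable toxicity. It already keeps the two apart: a grade 3 infusion reaction stops drug in Section 6.5.3.4, yet a first one without steroid prophylaxis that resolves within 6 hours is excluded in Section 9.4.1.

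**What to change.** Reconcile Sections 6.5.3.2, 6.5.3.3 and 6.5.3.4 with the Appendix 2 skin footnote. Give one instruction for suspected SJS/TEN and one for diagnosed SJS/TEN, say explicitly whether each depends on grade, and state both identically in the three subsections and the appendix. The clinical team chooses the rule; this review proposes none.

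The cost is a wording amendment to three subsections and, if needed, one footnote. It needs no new procedures, visits or patients, and the sample size is unaffected. Separately, and as an option rather than a correction, the sponsor may consider whether the lead-in toxicity definition in Section 9.4.1 should be aligned with whatever rule is adopted.

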# Neurological Adverse Event Management Algorithm

Rule out non-inflammatory causes. If non-inflammatory cause, treat accordingly and continue I-O therapy.

Patients on IV steroids may be switched to an equivalent dose of oral corticosteroids (e.g. prednisone) at start of tapering or earlier, once sustained clinical improvement is observed. Lower bioavailability of oral corticosteroids should be taken into account when switching to the equivalent dose of oral corticosteroids.
